Hospitalization information will be captured by participant self-report and medical record review. Self-report is valid and reliable, especially with inpatient care and recall periods less than one year¹⁰⁵; however, hospitalization data will also be collected from VA electronic medical records, and –where feasible– from non-VA providers. The study’s case report forms will contain detailed information about the index hospitalization and will note re-hospitalizations, rehabilitation unit admissions, and long-term care facility admissions. Specifically, the case report forms will record the total number of days of hospitalization. Hospitalizations of any type will be considered: there is no minimum time-frame for hospitalization and both admissions and observations will be considered as countable. In this study, hospitalizations associated with index implantation, re-implantation, or generator changes will not be considered as countable all-cause hospitalizations.

C. Device Data

ICDs monitor and store data on a wide range of parameters including battery and lead function, patient activity, heart rate, frequency of pacing, and most importantly tachyarrhythmia events. The ICD stores extensive data on all tachycardia events that trigger therapy including beat to

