Thus, CSP#592 will expect all devices to be so programmed at time of implant. Programming changes that depart from these parameters at time of implant (whether intentionally or unintentionally) will be considered protocol deviation. After day of implantation, programming changes will be allowed based on clinical indications, such as development of heart block, development of slow VT, and syncope with VT/VF. Ultimately, the programming parameters will be left to the discretion of the investigator.

5. Re-implantation

Patients who have previously had an ICD or pacemaker explanted will not be eligible for entry into this study. For patients receiving an ICD as part of CSP592, and then being explanted and re-implanted, e.g. if the study implantation becomes infected and the device is removed and then re-implanted, then no new ICD Implantation Case Report Form (Form 12) is to be completed; the second implantation procedure is to be documented via a Process Note and Site Data Edit Form (Form 22) when the device or procedure information needs to be updated (as well as SAE and Hospitalization Forms, as appropriate). Adverse Events will be collected after any implant procedure; AEs will be assessed in two different analyses: 1) 'index AEs', occurring in the 30 days following the first implantation procedure, and 2) 'all AEs', occurring in the 30 days after any implantation procedure.

C. Optimal Medical Therapy

1. Overview

Optimal Medical Therapy must be established prior to entry into the study, and will be documented at the time of Randomization. Notwithstanding this condition for entry, Study team members will be available to provide guidance on where to learn more about lifestyle modification, exercise training, and disease management as needed, so that every participant will be exposed to the basic skills required to sustain improved health and well-being. Participants will also be encouraged to discuss lifestyle modifications with their regular treating clinician; however, the instructions and –as applicable– educational materials provided by the Study Team will be the same as those that would be provided by the clinical care team outside of the study; there will be no study-wide materials provided. These activities comprise the field guidelines for primary prevention of cardiovascular disease and stroke. Details on these lifestyle principles follow.

2. Physical Activity

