Strict adherence to the protocol is expected of every participating center and monitored by the DMC, the Executive Committee and the Study Group. Data quality and the completeness of data retrieval, including the Screening Tracker, are closely monitored on an ongoing basis by the WH-CSPCC. The Study Biostatistician presents interim monitoring reports, overall and by site, to the Executive Committee and DMC that include the following types of information: recruitment of participants, characteristics of the population, completeness of data retrieval, and data quality. If a site is identified as an outlier in terms of data quality, a site conference call or site visit is initiated to assess the reasons that problems are occurring and how they can be corrected. If the problems continue, the site may be placed on probation or terminated from the study if the problems cannot be corrected.

F. Monitoring Participant Safety

The local site investigator is responsible for following adverse event reporting requirements as outlined below in the Protocol. These responsibilities include: 1) reviewing the accuracy and

completeness of all adverse events reported, 2) compliance with IRB policies for reporting adverse events and/or serious adverse events, and 3) closely monitoring research participants at for Adverse Events (AEs) or Serious Adverse Events (SAEs). All AEs and SAEs are recorded on the appropriate event form(s). Active monitoring of SAEs begin as soon as the study participant provides consent and continue until the participant completes follow-up. In this study, we will only monitor AEs for 30 days post-randomization (OMT arm) or 30 days post-implantation (OMT + ICD arm). We identify several SAEs that will not require immediate reporting to CIRB, in order to enable detection of clinically meaningful safety information. These SAEs include

- Bleeding/Hematoma
- Incisional pain
- Infection: ICD pocket or lead; requiring antibiotic treatment or explant
- Infection: Other, requiring antibiotic treatment
- Lead dislodgement
- Lead fracture
- Pacing parameters require lead replacement or revision
- Pneumothorax
- Myocardial infarction (MI)
- Stroke
- Tachyarrhythmia/atrial fibrillation

Unexpected SAEs will follow regulations for timely reporting to CIRB: All Serious Unanticipated Problems involving risks to subjects or others and all Serious

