- Complying with study policies as well as IRB policies for reporting adverse events, serious adverse events, and unanticipated adverse device effects
- Report to CSP all SAEs within 72 hours of becoming aware of the event
- Reporting to the IRB safety issues reported to the site by the Sponsor
- Closely monitoring research subjects for any new AEs, UADEs, and SAEs
- Maintaining clinic lists to facilitate near-real time event discovery
- Provide updates to Central Follow-Up Office upon event discovery and upon their request during event follow-up

B. Definitions

1. Adverse Event (AE)

An Adverse Event (AE) is defined as “any untoward physical or psychological occurrence in a human subject participating in research.” An AE can be any unfavorable and unintended event, including an abnormal laboratory finding, symptom, or disease associated with the research or the use of a medical investigational test article. While an AE does not necessarily have to have a

causal relationship with the research ¹²⁰, in CSP #592 AEs will be collected, and only for 30 days after implantation (within the ICD + OMT arm), or 30 days after randomization (OMT arm). We will also collect AEs for 30 days after any re-implantation procedure. For the purposes of this study, we are primarily interested in the following AEs:

- Discomfort at the implant site
- Cosmetic issues (e.g. scars, etc.)
- Psychological issues (e.g. apprehension of an activation, etc.)
- Technical issues related to the device (e.g. actions that may require re-implantation or a generator change)
- Delay angioedema with cough
- Rise in creatinine
- Fatigue
- Slow heart rate

Other adverse events –including those that may not necessarily have to have a causal relationship with this treatment– may also be collected.

2. Unanticipated (or Unexpected) Adverse Event (UAE)

An Unanticipated (or Unexpected) Adverse Event (UAE) is an AE that is new or greater than previously known, in terms of nature, severity, or frequency of occurrence, as documented in the protocol or other materials approved by IRB. Such materials may include, but are not limited to: the informed consent form, clinical investigator’s brochure, and product labeling ¹²⁰.

3. Unanticipated Adverse Device Effect (UADE)

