An Unanticipated Adverse Device Effect (UADE) means any serious adverse effect on health or safety or any life-threatening problem or death caused by, or associated with, a device, if that effect, problem or death was not previously identified in nature, severity, or degree of incidence in the investigational plan or application, or any other unanticipated serious problem associated with a device that relates to the rights, safety, or welfare of subjects ¹²¹.

All AEs and UADEs with a reasonable causal relationship to the investigative treatment should be considered at least “possibly related.” A definite relationship does not need to be established.

4. Serious Adverse Event (SAE)

An adverse event is considered a Serious Adverse Events (SAE) if, in the view of either the investigator or Sponsor, it results in any of the following outcomes:

- Death
- A life-threatening adverse event
- Inpatient hospitalization or prolongation of existing hospitalization
- A persistent or significant incapacity or substantial disruption of the ability to conduct normal life functions
- A congenital anomaly/birth defect
- Any other condition that, based upon medical judgment, may jeopardize the subject and require medical or surgical treatment to prevent one of the above outcomes.

In particular, this study will not consider any of the following as either an SAE or a hospitalization: index implantation of an ICD device, re-implantation of an ICD after explantation, or generator change.

All serious adverse events are collected, including those related and not related to the study intervention. All serious adverse events with a reasonable causal relationship to the investigative treatment should be considered “related”. All SAEs will be promptly reported by submission of the event into the CSP #592 data capture system within 72 hours of the site investigator being made aware of the event. Email notification of the submission will immediately be relayed by the CSP #592 data capture system to the Study Biostatistician, Clinical Research Pharmacist, and Study Chair. The CSPCRPCC will be responsible for evaluating all serious adverse events for participant safety concerns. Serious adverse events (as defined by CRF 312.32) that are **unanticipated and related to the investigational treatment** are expeditiously reported to the CSPCRPCC Director, CSPCC, CIRB, DMC, and all regulatory agencies.

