The Clinical Research Pharmacist and Study Biostatistician generate tabulations of adverse events and present a summary of all AEs and SAEs to the DMC on a schedule set by the DMC. The DMC also determines when they should be unblinded to treatment assignment in reviewing adverse event data. The Study Biostatisticians provides the appropriate data to the DMC at specified intervals for this purpose. Serious adverse events are reported on a regular basis to the DMC for their review. Unanticipated serious adverse events are reported to the DMC as soon as they become known based upon the consensus of the Principal Proponent, the Study Biostatisticians, the Director of the West Haven CSPCC, and the Study Pharmacist.

C. AE/UADE and SAE Monitoring and Reporting

AEs, UADEs and SAEs will be monitored at the study sites throughout the period of the study, beginning as soon the research subject signs the Informed Consent and continuing through end-of-study for each participant. Reportable AEs will be collected and recorded on the appropriate case report form; though we note that while AEs will be continually monitored for closure, new AEs will only be collected for the relevant 30-day window. All UADE and SAEs, including both those related to the study intervention and those not related to the study intervention will be collected and recorded on the appropriate case report form; new UADEs and SAEs will be collected throughout the study. For the purpose of safety monitoring, the study intervention is defined as “ICD implantation” or “Optimal Medical Therapy”.

All UADEs/SAEs require expedited reporting. An SAE case report form will be completed and submitted via the data capture system within 72 -hours of the Site Investigator initially becoming aware of the event. The Study Pharmacist at CSPCPRCC will be responsible for evaluating all SAEs/UADEs for participant safety concerns in a timely manner.

UADEs/SAEs that suggest evidence of a causal relationship between one of the study interventions and the adverse medical event and is unexpected will be reviewed by the Study Leadership Team (i.e., Study Chairperson, Study Biostatistician, Study Project Manager, and the Study Pharmacist) prior to notifying VA Central Office.

< This page left intentionally blank >

XV. BIostatistical Considerations

A. Sample Size

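### Leaving re-implantation and generator-change stays out of all-cause hospitalisation biases that exploratory comparison toward the ICD, and the SAP does not carry the rule

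*Combined protocol and SAP*

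**What the plan says.** Protocol XIV.B.4 (Serious Adverse Event) says that "this study will not consider any of the following as either an SAE or a hospitalization". Three procedures are then listed: the first implant, a new implant once a device has been taken out, and replacement of the generator.

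Protocol VI.B.4 (All-cause Hospitalization) opens the outcome to stays of every type, observation stays included. It then adds that "hospitalizations associated with index implantation, re-implantation, or generator changes will not be considered as countable all-cause hospitalizations".

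Protocol X.B.5 (Re-implantation) takes an infected device that is removed and replaced as its example. No second implantation form (Form 12) is completed. The procedure goes on a Process Note and, when device or procedure information changes, Form 22, "as well as SAE and Hospitalization Forms, as appropriate".

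Three other provisions bear on the point:

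- XII.F lists among SAEs "Infection: ICD pocket or lead; requiring antibiotic treatment or explant", together with lead dislodgement, lead fracture and lead replacement or revision. The list waives only immediate reporting to the central IRB; the events are still collected.
- XIV.B.1 names device technical problems among the AEs of main interest and adds: "We will also collect AEs for 30 days after any re-implantation procedure".
- XIV.C collects new SAEs and unanticipated device effects throughout the study, but for non-serious events "new AEs will only be collected for the relevant 30-day window".

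SAP sections 1.3.2.4 and 2.2.7.2 (hospitalisation) and 2.2.9 (safety) do not mention the exclusion.

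**The concern.** The planned index implant is part of the assigned treatment, so leaving it out is defensible. A re-implant or generator change is different: it happens later, because the participant has a device, and the participant experiences it as a hospital stay. An outcome called all-cause should contain it.

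Nearly all such stays occur in one arm, so removing them can only make the ICD arm look better. The phrase in VI.B.4 reaches any stay associated with the procedure. A long admission for device infection, explant and re-implant could therefore be dropped whole, days included.

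The arms are compared at the 0.05 level on number of hospitalisations, hospital days and proportion hospitalised (protocol XV.C.4.b, SAP 2.2.7.2). SAE proportions are also tested (XV.C.5, SAP 2.2.9), and the DMC may act on them (XV.B.5, SAP 2.3.3). Safety is part of the stated overall aim.

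**Working it through.** **1. Which events are lost, and from which count**

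| Event | SAE count | All-cause hospitalisation |
|---|---|---|
| Device infection leading to explant | Kept (XII.F) | Stay may be dropped if a re-implant is associated with it (VI.B.4) |
| Lead dislodgement, fracture or revision | Kept (XII.F) | Kept, unless associated with a listed procedure |
| Explantation | Not on the exclusion list | Not on the exclusion list |
| Re-implantation | Excluded | Excluded |
| Generator change | Excluded | Excluded |
| Late generator failure not judged serious | Not an SAE; also outside the 30-day AE window | Stay excluded if it ends in a generator change |

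The last row is the clearest SAE-side gap. The failure comes before the procedure, so an AE window that opens after a procedure does not catch it. XIV.B.1 reopens the window after re-implantation; no passage names generator change. Protocol III.G.4 gives a generator life of 5-7 years and follow-up is at most 5 years, so most changes within the trial would come before the stated life and are unlikely to be only routine upkeep.

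No SAP table shell restores the information. Tables 15-23 and 28-31 have no row for explantation, re-implantation or generator change.

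**2. How one-sided the exclusion is**

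Inputs (protocol XV.A.2, footnote to XV.A, SAP 2.1): control mortality 15% per year; hazard ratio 0.75; drop-in 2.5% per year; drop-out 1% in year 1 only; 731 per arm, made up of 51 pilot participants followed 5 years and 680 followed uniformly 2 to 5 years.

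Model: a two-state cohort in daily steps. The off-device death hazard is h = -ln(0.85) = 0.1625 per year; the on-device hazard is 0.75h. OMT participants move onto a device at -ln(0.975) per year; ICD participants move off at -ln(0.99) per year in year 1. Implant is taken at randomisation, with no loss to follow-up.

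The plan states no figure for this exclusion, so the check is against its projected deaths. The model gives 257.5 + 316.7 = 574, against 565 stated (1.6% high). Cumulative mortality is 43.3% and 35.2%, against 42.0% and 34.1% (about 3% high in relative terms). That is close enough for this purpose.

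Expected device-years:

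- ICD arm: 2,091
- OMT arm: 86, from about 48 crossovers (48/731, about 6.5%)
- ICD share: 2,091 / (2,091 + 86) = 96%

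**3. How many procedures are left out**

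The documents give no rate, so r per device-year is assumed. Procedures = r x device-years.

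| Assumed r | ICD arm | OMT arm |
|---|---|---|
| 1% | 20.9 | 0.9 |
| 2% | 41.8 | 1.7 |
| 3% | 62.7 | 2.6 |

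**4. Effect on the SAE proportion**

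Let p be the proportion with another SAE in either arm, and q the share of procedures whose cause is not itself a counted SAE. With a = r x 2,091/731 and c = r x 86/731, counting the procedures would widen the gap between arms by (1 - p) x q x (exp(-c) - exp(-a)), approximately.

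- q = 0: no change.
- q = 1, r = 1%, p = 80%: 0.2 x (0.9988 - 0.9718) = 0.5 points.
- q = 1, r = 3%, p = 40%: 0.6 x (0.9965 - 0.9178) = 4.7 points.

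With 731 per arm, the difference detectable with 80% power is 7.3 points at p = 40%, 7.1 at 60% and 5.6 at 80%. The exclusion alone would not usually decide that test.

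**The case against.** The strongest reply is that the rule excludes the procedure, not the complication. Device infection needing explant and lead failure remain SAEs, explantation is not excluded, and SAP Tables 18 and 19 show device infection and lead revision by arm with attribution to the device. In the protocol's own example the harm is already an SAE, so adding the re-implant could count one episode twice. A late malfunction that meets the seriousness criteria is collected at any time. X.B.5 also plans an AE analysis covering 30 days after any implantation procedure. All of this stands. A reader might infer from XIV.B.4 that ICD harm is understated across the SAE data; the documents do not support that.

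A reader might also infer that X.B.5 contradicts VI.B.4 and XIV.B.4. The wording "as well as SAE and Hospitalization Forms, as appropriate" can mean forms for the complication rather than for the re-implant, and collecting a form differs from counting an event. This is an ambiguity that sites may resolve differently. It concerns re-implantation only, since no passage asks for these forms after a generator change.

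Nor does the exclusion fall on one arm alone: planned drop-in puts about 4% of device-years in the OMT arm.

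Finally, hospitalisation is exploratory, and the primary outcome, death from any cause, is untouched. That limits the weight of the point but does not answer it. No rationale is given for leaving these stays out of an all-cause count, and the direction of the bias is fixed.

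**Conclusion.** The point holds for all-cause hospitalisation. As written, the rule removes stays that arise almost only in the ICD arm, so number, days and proportion are biased toward the ICD. For SAEs it holds only where the cause of the procedure goes unreported as an SAE, such as a late generator failure not judged serious.

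The size cannot be derived from the documents. At an assumed 1-3% per device-year, about 21-63 ICD-arm procedures are left out against about 1-3 under OMT. Treating each as a hospital stay is a further assumption, and no length of stay is given, so the missing days cannot be estimated. The SAE gap would move by 0 to about 5 points, with p assumed at 40-80%. The 96% share rests on the protocol's mortality, hazard-ratio and crossover assumptions.

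The firmer inconsistency is between documents: the protocol states the exclusion and the SAP does not, so an analyst working from the SAP would count whatever such stays had been collected.

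**What to change.** - In VI.B.4 and XIV.B.4, exclude only the index implant from all-cause hospitalisation. Count re-implantation and generator-change stays and their days, and report the version without them as a sensitivity analysis.
- State whether a first implant in an OMT participant (about 48 expected) is an index implant.
- State that the complication leading to a re-implantation or generator change is reported as an SAE when it meets the criteria, without also counting the procedure as a separate SAE.
- Reword X.B.5 to say which event each form records, and give the same instruction for generator change, so that VI.B.4, X.B.5 and XIV.B.4 agree.
- Put the rule in SAP 1.3.2.4, 2.2.7.2 and 2.2.9, and add a table of explantation, re-implantation and generator change by arm.

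The cost is wording in both documents, a few extra forms, one added table and one sensitivity analysis. The ICD hospitalisation figures will look slightly less favourable.
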